Visit Identifier Abbreviations used in this table may be found in Appendix 12 .	Screening	Baseline (Day 1)	Day 3	Day 5	Day 10	Day 14	Day 21	Day 34	LT F/U		ET (prior to Day 34)	Notes
									Week 12	Week 24		
Visit Window	Day -1 to Day 1	0 days	±1 day	±1 day	±1 day	±2 days	±2 days	±3 days	±7 days	±7 days	±5 days	
Optional PK sampling ([PF-07321332] collected via home health, site visit, or self-collected using Tasso; in a subset of participants, if feasible)			X									
 PK sample(s) will be collected either during in-person visit (a single blood sample collected at any time on either Days 2, 3, or 4) or self-collected by Tasso microsampling device (selected sites) at the following timepoints: 
 Day 2 before the evening dose, Day 3 after the morning dose at the following times: 1 sample between 30 to 90 minutes, 1 sample between 2 to 6 hours, and 1 sample 8 to 12 hours after the dose (the last sample should be collected before the evening dose). Refer to Section 8.4.
RANDOMIZATION		X										
STUDY INTERVENTION												
Study intervention administration		Day 1 through Day 5 (10 doses total)										
 If 1 dose was administered on Day 1, study intervention administration should end on Day 6. See Section 6.1
STUDY PROCEDURES & ASSESSMENTS												
Collect/update secondary contacts		X		X	X	X	X	X	X			
 The investigator will capture contact information for at least 2 individuals who the site can contact if the participant is unable to be reached after multiple attempts. At baseline, the investigator will also request contact information for any household members who may be eligible to participate in Study C4671006
Record supplemental oxygen requirements	X	X		X	X	X	X	X			X	
 See Section 8.1.4.

Visit Identifier Abbreviations used in this table may be found in Appendix 12 .	Screening	Baseline (Day 1)	Day 3	Day 5	Day 10	Day 14	Day 21	Day 34	LT F/U		ET (prior to Day 34)	Notes
									Week 12	Week 24		
Visit Window	Day -1 to Day 1	0 days	±1 day	±1 day	±1 day	±2 days	±2 days	±3 days	±7 days	±7 days	±5 days	
Study kit dispensed and participant instructed on its use		X										

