Participant-completed study diary (COVID-19 signs and symptoms and global impression questions)		Every day from Day 1 through Day 28										
 See Section 8.1.1 and Section 8.1.5.3. Global impression questions will be answered every day from Day 1 through Day 28 after COVID-19 signs and symptom diary is completed. Global impression questions will only be assessed in participants, as available.
WPAI				X		X			X	X		
 Will be assessed in participants, as available. See Section 8.1.5.1.
EQ-5D-5L		X		X		X		X	X	X		
 Will be assessed in participants, as available. See Section 8.1.5.2.
Exit interview								X				
 Exit interviews will be conducted by telephone and are to occur after the Day 34 visit in a select group of US English-speaking participants (up to 50) at selected sites. See Section 8.1.6.
Staff review of study diary				X	X	X	X	X			X	
 See Section 8.1.1.
Participant-completed study intervention log		Day 1 through Day 5										
 Study intervention log should be completed daily on Days 1 through Day 6 if only 1 dose was administered on Day 1. See Section 6.4.
Record COVID-19-related medical visits				X	X	X	X	X				
 COVID-19 related medical visits a participant has attended since the last assessment will be collected. See Section 8.1.2.
Retrieval of unused study intervention and empty study intervention containers				X		[X]		[X]			X	
 If the Day 5 visit is conducted prior to last dose of study intervention, the study intervention log, empty study intervention containers, and unused study intervention should be returned at the next in-person visit. See Section 6.4.

Visit Identifier Abbreviations used in this table may be found in Appendix 12 .	Screening	Baseline (Day 1)	Day 3	Day 5	Day 10	Day 14	Day 21	Day 34	LT F/U		ET (prior to Day 34)	Notes
									Week 12	Week 24		
Visit Window	Day -1 to Day 1	0 days	±1 day	±1 day	±1 day	±2 days	±2 days	±3 days	±7 days	±7 days	±5 days	

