7.2. Participant Discontinuation/Withdrawal From the Study

A participant may withdraw from the study at any time at his/her own request. Reasons for discontinuation from the study include the following:

- Refused further study procedures;
- Lost to follow-up;
- Death;
- Study terminated by sponsor.

At the time of discontinuing from the study, if possible, an early discontinuation visit should be conducted. See the [SoA](#) for assessments to be collected at the time of study discontinuation and follow-up and for any further evaluations that need to be completed.

The early discontinuation visit applies only to participants who are enrolled/randomized and then are prematurely withdrawn from the study. Participants should be questioned regarding their reason for withdrawal.

If a participant withdraws from the study, he/she may request destruction of any remaining samples taken and not tested, and the investigator must document any such requests in the site study records and notify the sponsor accordingly.

If the participant withdraws from the study and also withdraws consent (see Section 7.2.1) for disclosure of future information, no further evaluations should be performed and no additional data should be collected. The sponsor may retain and continue to use any data collected before such withdrawal of consent.

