8.1.2. COVID-19-Related Medical Visit Details

Details of participants' COVID-19-related medical visits (ie, hospitalization, practitioner's office, home healthcare services, telemedicine, urgent care, emergency room ≤ 24 hours,

extended care facility stay) will be collected during study visits, including level of care (ICU status) and dates of utilization, including admission and discharge, as applicable.

Hospitalization is defined as >24 hours of acute care, in a hospital or similar acute care facility, including Emergency Rooms or temporary facilities instituted to address medical needs of those with severe COVID-19 during the COVID-19 pandemic. This includes specialized acute medical care unit within an assisted living facility or nursing home. This does not include hospitalization for the purposes of public health and/or clinical trial execution.

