The estimand for the number of COVID-19-related medical visits through Day 28 is the difference in estimated rate of number of COVID-19 related medical visits through Day 28 in nonhospitalized adult patients with COVID-19 who are at low risk of progression to severe

disease and were treated ≤ 5 days after COVID-19 symptom onset. This will be estimated without regard to adherence to randomized treatment.

The statistical methodology for this endpoint will be as follows:

The number of COVID-19 related medical visits will be analyzed with a negative-binomial regression model, using the log-total number of days of data collection as the participant offset variable. The resulting analysis will provide the estimated difference in rate of medical visits between treatment groups and the associated 95% CI.

Number of days in hospital and ICU stay in participants with COVID-19-related hospitalization through Day 28

Summary statistics for this endpoint will be provided in support of the number of COVID-19-related medical visits through Day 28.

Details on the definitions and analyses of the following secondary endpoints will be described in the SAP.

- Time (days) to sustained resolution of all targeted COVID-19 signs/symptoms through Day 28.
- Proportion of participants with severe signs/symptoms attributed to COVID-19 through Day 28.
- Duration of each targeted COVID-19 sign/symptom.
- Progression to a worsening status in 1 or more self-reported COVID-19 associated symptoms through Day 28.
- Proportion of participants with a resting peripheral oxygen saturation $\geq 95\%$ at Days 1 and 5.
- Proportion of participants with death (all cause) through Week 24.
- PF-07321332 PK in plasma and whole blood (if feasible).
- Viral titers measured via RT-PCR in nasal swabs over time.

CCI

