10.3.1. Definition of AE

AE Definition

• An AE is any untoward medical occurrence in a patient or clinical study participant, temporally associated with the use of study intervention, whether or not considered related to the study intervention.• Note: An AE can therefore be any unfavorable and unintended sign (including an abnormal laboratory finding), symptom, or disease (new or exacerbated) temporally associated with the use of study intervention.

Events Meeting the AE Definition

• Any abnormal laboratory test results (hematology, clinical chemistry, or urinalysis) or other safety assessments (eg, ECG, radiological scans, vital sign measurements), including those that worsen from baseline, considered clinically significant in the medical and scientific judgment of the investigator. Any abnormal laboratory test results that meet any of the conditions below must be recorded as an AE:
• Is associated with accompanying symptoms.• Requires additional diagnostic testing or medical/surgical intervention.• Leads to a change in study dosing (outside of any protocol-specified dose adjustments) or discontinuation from the study, significant additional concomitant drug treatment, or other therapy.• Exacerbation of a chronic or intermittent preexisting condition, including either an increase in frequency and/or intensity of the condition.• New condition detected or diagnosed after study intervention administration, even though it may have been present before the start of the study.• Signs, symptoms, or the clinical sequelae of a suspected drug-drug interaction.• Signs, symptoms, or the clinical sequelae of a suspected overdose of either study intervention or a concomitant medication. Overdose per se will not be reported as an AE or SAE unless it is an intentional overdose taken with possible suicidal/self-harming intent. Such overdoses should be reported regardless of sequelae.

Events **NOT** Meeting the AE Definition

- Any clinically significant abnormal laboratory findings or other abnormal safety assessments that are associated with the underlying disease, unless judged by the investigator to be more severe than expected for the participant's condition.
- The disease/disorder being studied or expected progression, signs, or symptoms of the disease/disorder being studied, unless more severe than expected for the participant's condition.

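### The schedule omits the COVID-19-related medical-visit record at the early termination visit, so outpatient visits since the last contact are not specifically asked about and admissions rest on SAE reporting

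*Protocol*

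**What the plan says.** In Protocol 1.3 the row "Record COVID-19-related medical visits" is marked at Days 5, 10, 14, 21 and 34. Its cells for Week 12, Week 24 and ET are empty. The note to the row gives the recall period: "COVID-19 related medical visits a participant has attended since the last assessment will be collected".

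Other rows of the same table do carry an ET mark. Among them are "Record supplemental oxygen requirements", "Staff review of study diary", the vital status check, concomitant medications and AE monitoring.

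Protocol 7.2 says that when a participant leaves the study, "if possible, an early discontinuation visit should be conducted", and refers the site to the schedule for what to collect. Protocol 8.1.2 counts hospitalisation, office, home-care, telemedicine, urgent-care and emergency-room contacts as medical visits and says that their details "will be collected during study visits, including level of care (ICU status) and dates of utilization, including admission and discharge, as applicable". It does not name the visits.

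Protocol 9.3.3 analyses the visit count with a negative binomial model "using the log-total number of days of data collection as the participant offset variable". SAP 5.2 lists this count, with hospitalisation or death, as one of two key secondary endpoints. SAP Appendix 1 does not impute missing data for it.

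**The concern.** Each medical-visit record looks back only to the previous one. If the question is not put at ET, a participant who leaves between scheduled assessments is not asked about the final interval. Both key secondary endpoints draw on this record: the visit count directly, and the hospitalisation component of hospitalisation or death, which is the endpoint that the increase to 1980 participants is meant to serve.

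Two consequences would matter. An admission not captured elsewhere drops out of the Kaplan-Meier estimate, because the participant is censored. For the visit rate, days between the last record and the ET contact could enter the offset while visits made on those days were never asked about, which would understate the rate.

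**Working it through.** **1. Is the blank cell real?** The row was read cell by cell against the twelve column headings (Screening, Baseline, Days 3, 5, 10, 14, 21 and 34, Week 12, Week 24, ET, Notes). It has all twelve cells, and the ET cell is empty. The diary-review row has the same marks at Days 5 to 34 and does have an X at ET, so the blank is not a column lost in text extraction.

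**2. Does other text restore the item?** Protocol 7.2 defers to the schedule. Protocol 8.1.2 speaks of study visits in general. Neither adds the record at ET.

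**3. What else reaches the final interval?**

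| Item | Route at ET | Limit of the route |
|---|---|---|
| Death | Vital status check | None for this purpose |
| Admission | AE/SAE monitoring; inpatient hospitalisation is an SAE criterion (Protocol 10.3.2) | Usually an overnight stay, against more than 24 hours of acute care in 8.1.2; ICU level and utilisation dates not specified |
| Office, home-care, telemedicine, urgent-care and short emergency-room visits | No dedicated route | Open-ended AE questioning only (8.3.2) |

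The SAE route also needs an AE to start from. Protocol 10.3.1 lists among events that are not AEs "The disease/disorder being studied or expected progression, signs, or symptoms of the disease/disorder being studied, unless more severe than expected".

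**4. How many participants?** The plan's enrolment figure reproduces: 1140 + 740 = 1880, and 1880 / 0.95 = 1979, stated as about 1980 (Protocol 9.5). Leavers: 0.05 × 1980 = 99. This is an upper bound for the group affected. It includes people who leave after Day 28, at a scheduled visit, or without an ET contact. Those who only stop study drug stay on the normal schedule (Protocol 7.1).

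**5. How many hospitalisation or death events fall in the unasked interval?** Assume that all 99 leave before Day 28, risk is uniform over 28 days, and the arms are pooled. Then expected events = 99 × risk × gap / 28. The lower risk is the planned 26/1880 = 1.4%. The higher is the placebo rate at the first interim, 8/329 = 2.4% (Protocol 2.2.2).

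| Gap (nominal) | Risk 1.4% | Risk 2.4% |
|---|---|---|
| 5 days (Day 5 to 10) | 0.24 | 0.43 |
| 7 days (Day 14 to 21, or Day 21 to 28) | 0.34 | 0.60 |
| 13 days (Day 21 to 34) | 0.64 | 1.12 |

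The range is about 0.2 to 1.1 events. The upper end is generous: it applies the placebo rate to both arms and uses a gap that runs past Day 28, where the endpoint stops. One event is 1/26 = 3.8% of the target. In a simple unconditional two-proportion calculation (940 per arm, 70% reduction), power moves from 0.79 with 26 events to 0.77 with 25. The plan's 90% is conditional on second-interim data that the documents do not give, so it cannot be reproduced.

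**6. How much visit-count follow-up is unasked?** With a 7-day gap for every leaver, 99 × 7 = 693 person-days. Completers alone contribute 1881 × 28 = 52,668. The ratio is 693 / 52,668 = 1.3%. The documents give no visit rate, so the number of visits missed cannot be estimated.

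**The case against.** The strongest reply is that admissions are not left unasked, and this stands. AE/SAE monitoring is scheduled at ET. Active collection runs at least 28 days after the last dose and, for a withdrawal, ends early only if consent for future information is also withdrawn (Protocol 8.3.1). Protocol 10.3.2 says to treat the AE as serious when hospitalisation is in doubt. Section 8.3.7 exempts no disease-related events, and 8.3.8.1 requires clinical sequelae of lack of efficacy to be reported. An admission may well count as more severe than expected in this population. ET also records oxygen support. A reader might infer from the blank cell that hospitalisations are simply lost for leavers. The documents do not support that. What remains is a difference in definition and detail.

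A reader might also see Protocol 8.1.2 as contradicting the schedule. It does not, because it names no visits.

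A larger loss is tempting to imagine but has no basis in the documents. Five missed placebo events would need about 5/49.5 = 10% of placebo leavers to be admitted within one 7-day gap. The interim placebo rate gives 2.4% × 7/28 = 0.6%, about 17 times lower. The 18% discontinuation assumption belongs to the initial symptom-endpoint calculation; the plan for 1980 uses 5%.

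The sensitivity analysis that imputes an event when last data precede Day 21 gives some cover, but it is worded for loss to follow-up. Whether it reaches withdrawals with an ET contact is unclear.

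Finally, days of data collection can naturally be read as ending at the last visit record. The offset is therefore ambiguous, and a bias is not demonstrated.

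**Conclusion.** The omission is real and no other text repairs it. For participants who leave the study and have an ET contact, outpatient, telemedicine, urgent-care and short emergency-room visits since the last assessment are not specifically elicited. Admissions in that interval depend on SAE reporting under a different definition. Death is covered.

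The likely effect is small: at most about 99 participants, and about 0.2 to 1.1 expected hospitalisation or death events against 26. Even those would be missed only if SAE reporting also failed to capture them. The estimate rests on uniform risk and on withdrawal being unrelated to admission. If people leave because they are admitted, it would be higher, by an amount the documents do not let one calculate. Confidence is high on the blank cell and lower on its effect. The change is still worth making, because it completes the data for a key secondary endpoint at little cost.

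**What to change.** - In Protocol 1.3, mark the medical-visit row in the ET column, covering the time from the last assessment to the ET contact with the details listed in 8.1.2.
- For participants already terminated, ask sites to complete the same CRF page from source records up to the ET date, where consent allows, and reconcile it with SAE records.
- In SAP 5.2.4 and 6.2.5, state that the offset ends at the last date on which medical visits were actually recorded.

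The cost is one existing CRF page at a contact already planned, a limited retrospective site query, and one sentence in the SAP. The query cannot help where no source record exists or consent has been withdrawn, and the ET mark cannot help participants who have no ET contact.

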2. INTRODUCTION

PF-07321332, a potent and selective SARS-CoV-2 3CL protease inhibitor, is being investigated as an oral antiviral treatment of COVID-19.

2.1. Study Rationale

The purpose of this study is to evaluate the efficacy and safety of PF-07321332/ritonavir for the treatment of nonhospitalized, symptomatic, adult participants with COVID-19 who are at low risk of progression to severe illness.

2.2. Background

In December 2019, COVID-19 was identified as a new, potentially fatal, respiratory infection caused by the novel coronavirus, SARS-CoV-2. The WHO declared COVID-19 a Public Health Emergency of International Concern² on 30 January 2020 and further characterized the disease outbreak as a pandemic on 11 March 2020.³ As of 12 January 2022, at least 315 million cases have been confirmed worldwide, and at least 5.5 million deaths have occurred.⁴

COVID-19 manifests as a wide range of illness, from asymptomatic infection to severe pneumonia, ARDS, and death. Although most (approximately 80%) cases are asymptomatic or mild,⁵ patients who are hospitalized with COVID-19 may have significant morbidity and mortality,^{6,7} and are at increased risk of developing complications such as severe inflammation associated with elevations in proinflammatory cytokines, ARDS, acute cardiac injury, thromboembolic events, hypercoagulability, and/or kidney injury.⁸⁻¹¹ Moreover, other comorbidities, such as hypertension, obesity, and diabetes, as well as older age and male sex increase the risk for worse outcomes.⁶

Although there are symptomatic and/or supportive treatments for COVID-19, few antiviral drugs are available or in late-stage development to help treat COVID-19 in patients with mild to moderate COVID-19. Existing compounds, such as hydroxychloroquine and lopinavir/ritonavir, have been evaluated as potential treatment options for COVID-19, but have not demonstrated benefit or efficacy beyond SoC.¹²⁻¹⁴ The FDA has approved IV remdesivir,¹⁵ an antiviral drug with activity against SARS-CoV-2, for hospitalized patients with COVID-19 and for the treatment of mild to moderate COVID-19 in high-risk nonhospitalized patients.¹⁶ However, remdesivir monotherapy may not be sufficient in all subsets of patients¹⁷ across the COVID-19 spectrum or has shown modest effects.^{18,19} Favipiravir is currently under investigation for its activity against SARS-CoV-2 due to its broad-spectrum activity against various RNA viruses^{20,21} and has been approved in India and Russia to treat mild to moderate COVID-19.²² Although favipiravir has been generally well tolerated in clinical studies primarily for the treatment of the influenza virus, teratogenic findings in multiple animal species at exposures comparable to those achieved with the dosage regimen to treat influenza have limited its clinical use.²⁰

Three IV-administered mAb based regimens have received EUA for treatment of COVID-19 in the outpatient setting for high risk persons on the basis of observed reductions in hospitalizations and deaths in placebo-controlled randomized controlled trials.²²⁻²⁴

Eligibility for mAbs is limited to persons meeting EUA-defined criteria of being at high risk for progression to severe COVID-19 or hospitalization, may only be administered in settings in which health care providers have immediate access to medications to treat a severe infusion reaction and require patients be monitored during administration and for at least 1 hour after infusion is complete. In addition, as the mAb based regimens primarily target the variable spike protein, there is ongoing risk that the continued emergence of SARS-CoV-2 variants will negatively impact the efficacy of mAb based regimens.

In December 2021, the FDA granted EUA for a 5 day course of treatment for 2 separate oral antiviral agents, PF-07321332 (nirmatrelvir)/ritonavir and molnupiravir, for the treatment of COVID-19 in adult and pediatric patients 12 years of age and older who weigh at least 40 kilograms, with mild to moderate COVID-19 who are at high risk for progressing to severe illness. Molnupiravir is not recommended during pregnancy, as findings from animal reproduction studies showed that molnupiravir may cause fetal harm when administered to pregnant individuals. In January 2022, remdesivir received approval for this same population. This treatment is administered by IV infusion over 3 days for nonhospitalized patients with mild to moderate COVID-19 who are at high risk for progressing to severe illness.

There is thus a high unmet need for antiviral agents that could be used for the treatment of nonhospitalized persons with COVID-19. Such agents, particularly those that target highly conserved viral targets, don't require administration in a healthcare setting, and with a risk/benefit profile supportive of administration to a broad patient population will significantly add to the treatment armamentarium for COVID-19.

The coronavirus 3CL protease is a virally encoded enzyme that is critical to the SARS-CoV-2 replication cycle, analogous to other obligatory virally encoded proteases (eg, HIV Protease, HCV Protease).²⁵ Mutagenesis experiments with other coronaviruses and picornaviruses that are related to SARS-CoV-2 (picornavirus-like supercluster) have demonstrated that the activity of the 3CL protease (or the corresponding picornaviral 3C enzyme) is essential for viral replication. No close human analogs of coronavirus 3CL enzymes are known, suggesting that appropriate 3CL inhibitors may function as selective inhibitors of SARS-CoV-2 and other coronaviruses as therapeutic agents.

PF-07321332, a potent and selective inhibitor of the SARS-CoV-2 3CL protease, is being developed as an oral treatment in patients with COVID-19.

In this study, PF-07321332 will be coadministered with ritonavir. Ritonavir is a strong CYP3A4 inhibitor, and is being coadministered with PF-07321332 to achieve exposures sufficient to suppress viral replication through the entire dosing interval (ie, $C_{trough} > EC_{90}$). Ritonavir is not expected to have any antiviral activity against the SARS-CoV-2 virus.

